**Examples of baseline and primary endpoint photographs (any response):**

**W0**

**W0**

**W24**

**W24**

**Examples of baseline and primary endpoint photographs (nonresponse):**

**W0**

**W0**

**W24**

**W24**

## 20 Secondary outcome measures

### 20.1 Hemangioma Activity Score

The key secondary outcome measure was the Hemangioma Activity Score (HAS), which was measured at baseline and at 1, 4, 12 and 24 weeks using digital photographs. The photographs of the target hemangioma acquired at each visit were sent to the CIS. The consecutive digital photographs were assessed by centralized evaluation at West China Hospital of Sichuan University. Three trained investigators who were unknown to the study group assignments independently evaluated the digital photographs taken at baseline and the follow-up visits. According to previous reports, changes in an individual HAS could be used to evaluate the effect of treatment. Baseline scores were subtracted from posttreatment scores to obtain the change in HAS or the decrease in hemangioma proliferative activity after treatment.

The HAS system has three scoring forms, including the degree of deep swelling, the color of the hemangioma, and the ulceration assessment:

(1) Assessment of the degree of swelling (or protrusion or elevation). A proliferating superficial or mixed IH can present as a protrusion with an overlying red tint. If there is visible swelling (or protrusion or elevation), it was scored as follows:

-Six points if the swelling (or protrusion or elevation) was tense;

-Four points if the swelling (or protrusion or elevation) was 'neutral' (i.e., not tense or less tense) at baseline or had <50% reduction at follow-up;

-Two points when the swelling (or protrusion or elevation) was reduced by 50% or more at follow-up; or

-Zero points when there was no more visible swelling (or protrusion or elevation) at a follow-up.

If the patient had superficial IH and showed no visible evidence of swelling (or protrusion or elevation) at baseline, this step was omitted or we set the point as 0. However, the score for no swelling (which was zero) affected the final score.

(2) Assessment of the color of the IH. The hemangioma color was assessed by blinded central investigators. A bright-red (or shining-red) color suggested that the hemangioma was very actively proliferating. A diminishing red color on the surface was seen during the phases of involution. It is therefore possible that different scores might have been applied to different phases of the same hemangioma. A bright-red hemangioma received the highest score.

---

The intensities of hemangioma color were rated from 5 through 0:

- Five points if the hemangioma lesion was bright red all over;
- Four points if only the edge of the hemangioma lesion was bright-red;
- Three points if the hemangioma lesion was matte red or reddish-purple (totally or partially) or if the hemangioma lesion was matte red only at the edge;
- Two points if the hemangioma lesion was totally or partially blue or showed blue shining through in deep lesions;
- One point if the hemangioma lesion was totally or partially gray;
- Zero points if the hemangioma lesion was totally or partially skin-colored after involution. At this stage, the hemangioma color was imperceptible.

If the hemangioma lesion was bright red, whereas the edge was not scored, then a bright-red edge was only be scored when the rest of the hemangioma lesion was not bright red. The total number was divided by the number of items scored to give to the mean score. Even the score for a normal skin color (which will be zero) would have an effect on the final score and thus was scored only if the hemangioma lesion had previously been another color.

(2) Assessment of the ulceration. If ulcerations were visible, additional points were given. The scoring system for an ulcerated hemangioma was as follows:

- 0.5 point for an ulcer  $\leq 1.0 \text{ cm}^2$ ;
- One point for an ulcer  $> 1.0 \text{ cm}^2$  but  $< 25 \text{ cm}^2$ ;
- Two points for an ulcer  $\geq 25 \text{ cm}^2$ .

Overall, for an individual hemangioma lesion, the HAS scale ranges from 0 to 8. Several examples of HAS system scoring are shown in eFigures 8 and 9. The HAS system scoring for these digital photographs is illustrated in eTable 3.

## ***20.2 Successful initial response***

A successful initial response was assessed by using HAS in the intention-to-treat population. A successful initial response was defined as an HAS decrease at 1 week after treatment. Previous studies demonstrated that HAS decreases over time after  $\beta$ -blocker treatment, with a dramatic drop occurring in the first week, indicating an immediate therapeutic response. HAS can reflect the rapid effect of  $\beta$ -blocker (either propranolol or atenolol) therapy shortly after initiation.

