### 25.4 Secondary outcome analyses

Quantitative variables were compared with Student's unpaired t-test, paired t-test, Wilcoxon rank sum test (Mann-Whitney  $U$  test), or generalized linear mixed models (GLMM). GLMMs were employed to compare the difference between the two groups in HAS changes from baseline to 6 months. Categorical variables were analyzed with Fisher's exact test or a chi-square test, and 95% confidence intervals were calculated. Kaplan-Meier curves were used to visualize the time to treatment discontinuation.

All secondary outcomes were analyzed based on the intention-to-treat principle without imputation of missing values.

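### Early effect is compared only as the proportion with any HAS decrease at week 1; no week-1 contrast of the graded score is prespecified, which costs power if the drugs differ in the size of the drop

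*Combined protocol and SAP*

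**What the plan says.** Section 20.1 makes the graded score the leading secondary outcome: "The key secondary outcome measure was the Hemangioma Activity Score (HAS), which was measured at baseline and at 1, 4, 12 and 24 weeks". It is read from photographs by three blinded central assessors. For a single lesion "the HAS scale ranges from 0 to 8", and change is computed on that scale: "Baseline scores were subtracted from posttreatment scores to obtain the change in HAS".

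Section 20.2 adds a separate outcome for early effect: "A successful initial response was defined as an HAS decrease at 1 week after treatment". No minimum size of decrease is required. The same paragraph reports from earlier studies that HAS falls over time on a beta-blocker, "with a dramatic drop occurring in the first week, indicating an immediate therapeutic response", and presents HAS as able to show how fast either drug acts.

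Section 25.4 gives two relevant analyses. For the graded score: "GLMMs were employed to compare the difference between the two groups in HAS changes from baseline to 6 months". For yes/no outcomes such as the one in 20.2: "Categorical variables were analyzed with Fisher's exact test or a chi-square test, and 95% confidence intervals were calculated". It also lists t-tests and the Wilcoxon test for quantitative variables in general. Neither 20.2 nor 25.4 names a between-arm comparison of the graded HAS at week 1, and neither states power for the week-1 outcome.

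**The concern.** Early effect is a question that the plan chose to ask, and the data to answer it in full are collected. The designated comparison keeps only the sign of the change, so a half-point fall and a fall of several points count alike. If most infants improve in the first week, which the paragraph in 20.2 suggests without giving a proportion, the cut at zero lies in the tail of the distribution of change. A cut there discards the most information.

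At stake is the reading of the early-effect result. Suppose one drug lowers HAS less than the other in week 1 but still lowers it in most infants. The two success rates would then be close, for example 90% against 84% in the calculation below, and a non-significant chi-square test could be reported as similar early response. A difference in mean change with its confidence interval would show how large a gap the data still allow.

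**Working it through.** **The plan's own figure.** There is none to reproduce for week 1. The 180 per group in section 12 belongs to the week-24 noninferiority comparison. It can be reproduced if the response rate is taken as 80% in both arms, a value chosen from inside the stated 70-100%: n = (1.960 + 1.282)² × 2 × 0.80 × 0.20 / 0.15² = 149.4, rounded up to 150, and 150 × 1.2 = 180. It is used below only as the number of infants available.

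**Inputs from the documents.** 1:1 allocation, two-sided 0.05, 180 per arm, 20% dropout (180 × 0.8 = 144 per arm), cut at any decrease.

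**Inputs assumed, because the documents give none.** Week-1 change in HAS is normal with the same SD in both arms; the arms differ by a mean shift of d = 0.30 SD; the share decreasing in the better arm, p₁, is 70%, 80%, 90% or 95%.

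**Step 1, graded change.** Power = Φ(d√(n/2) − 1.96). For n = 180: 0.30 × √90 = 2.846; 2.846 − 1.96 = 0.886; Φ(0.886) = 81%.

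**Step 2, cut at zero.** The other arm's share is p₂ = Φ(Φ⁻¹(p₁) − d). Power = Φ((p₁ − p₂ − 1.96·SE₀)/SE₁), where SE₀ uses the pooled proportion and SE₁ the separate ones.

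Worked for p₁ = 90%: p₂ = Φ(1.2816 − 0.30) = 83.7%; difference 0.0632; SE₀ = 0.0356; SE₁ = 0.0355; (0.0632 − 1.96 × 0.0356)/0.0355 = −0.185; Φ(−0.185) = 43%.

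| Share decreasing, better v other arm | Graded, 180 per arm | Cut at zero, 180 per arm | Graded, 144 per arm | Cut at zero, 144 per arm |
|---|---|---|---|---|
| 70% v 59% | 81% | 60% | 72% | 51% |
| 80% v 71% | 81% | 54% | 72% | 46% |
| 90% v 84% | 81% | 43% | 72% | 35% |
| 95% v 91% | 81% | 31% | 72% | 26% |

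At 180 per arm the loss runs from 81 − 60 = 21 points to 81 − 31 = 50 points. With d = 0.35 the pattern is the same: 91% graded against 73%, 68%, 55% and 41%.

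**Step 3, why the loss grows.** For a small shift, the efficiency of the cut relative to the graded score is φ(z)²/(p(1 − p)), with z = Φ⁻¹(p). It is 64% when half of infants decrease, 58% at 70%, 49% at 80%, 34% at 90% and 22% at 95%.

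**Step 4, scores in half-point steps.** Simulation with the change rounded to 0.5, a shift of 0.35 SD, 180 per arm and 91% against 84% decreasing gives 90% power for the t-test, 89% for Wilcoxon, 52% for chi-square and 46% for Fisher. Rounding and the choice of graded test do not alter the picture.

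**Step 5, a model in which the loss reverses.** Let the arms differ only in who decreases at all, 90% against 80%, with an assumed mean drop of 2 and SD of 1 among those who decrease.
- Yes/no test: SE₁ = √((0.09 + 0.16)/180) = 0.0373; SE₀ = √(2 × 0.85 × 0.15/180) = 0.0376; (0.10 − 1.96 × 0.0376)/0.0373 = 0.705; power 76%.
- Graded test: mean difference 0.10 × 2 = 0.20; variances p × 1 + p(1 − p) × 4 = 1.26 and 1.44; SE = √(2.70/180) = 0.1225; 0.20/0.1225 − 1.96 = −0.33; power 37%.
- Simulation with half-point scores gives about 77% against 40%.

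**The case against.** Four objections carry weight.

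**The graded score is not thrown away.** A reader might infer from 20.2 that the week-1 scores go unused beyond their sign. The documents do not support that. Graded HAS is the key secondary outcome, week 1 is one of its visits, and the model wording in 25.4 can be read as covering the whole course to 6 months. What is missing is narrower: no week-1 contrast is named, so the yes/no test is the only comparison designated for early effect.

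**The size of the loss is assumed.** The normal model, the shift and the success rates are not in the plan, and the phrase about a first-week drop describes earlier studies without giving a proportion. Step 5 shows that the direction can reverse. HAS is also coarse. A simulation restricted to a few values (0, −0.5, −1, some with −1.5; proportional odds 0.55-0.6; 180 per arm, all assumed) gave a loss of about 4-8 points at 70% success and 10-19 at 80%, though still 33-37 at 90%. This stands: the loss is conditional and must be shown as a range.

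**Noninferiority does not come into it.** A reader might infer that an insensitive week-1 test helps the trial reach its noninferiority claim. It does not. The margin, hypotheses and sample size in section 12 concern the week-24 response only. Section 25.4 also provides 95% confidence intervals for categorical comparisons, so imprecision at week 1 would be visible.

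**The yes/no outcome answers its own question.** Whether an infant has begun to respond is simple and easily read, and the lack of a cited source for a cut at zero is not an error. This stands as a reason to keep reporting the outcome. It does not explain why the size of the early effect has no prespecified comparison.

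**Conclusion.** The point holds in a limited form. The plan designates one comparison for early effect, that comparison ignores the size of the drop, and no week-1 contrast of the graded score is stated although the data and a model are in place. If the drugs differ by a shift in the size of the first-week change, the cut at zero costs about 21 to 50 points of power at 180 per arm (0.3 SD assumed, 70% to 95% decreasing in the better arm).

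The documents do not support saying that power is necessarily lost: the week-1 mean, SD and success rate are unknown, and a difference confined to whether any decrease occurs is better detected by the yes/no test. This is a secondary outcome for which the plan promises no power, so no stated figure is wrong. It is a worthwhile improvement, not a threat to the trial's main result.

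**What to change.** In 20.2 and 25.4, prespecify the between-arm difference in mean HAS change at week 1, with its 95% CI, as the main analysis of the size of the early effect. Take it as the week-1 contrast from the longitudinal HAS model already planned, and state that the model uses the visits at weeks 1, 4, 12 and 24. Keep the proportion with any HAS decrease and report it beside the contrast with its own 95% CI, so that a difference in who responds at all would still be seen.

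The cost is one sentence in each section. No new visit, photograph, reading or patient is needed. The small downside is one further secondary contrast to report.

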## ***20.3 Quality of life***

---

Quality of life (QOL) was measured at baseline and week 48.

#### *20.3.1 Quality of life instrument for IH*

The Quality of life instrument for IH (IH-QOL), which was developed by Sarah L Chamlin et al, was designed to measure the impact of treatment on IH patients and their parents. This module consists of 4 domains and 29 items. The domains include physical symptoms of the patient (4 items), social functioning of the patient (5 items), social and psychological functioning of the caregiver (10 items), and emotional functioning of the caregiver (10 items). IH-QOL is self-administered by the patients' parents and takes approximately 5 minutes to complete. The Chinese Mandarin Version of IH-QOL has previously been translated according to standardized procedures, which consist of 4 steps: forward translation (Chinese), backward translation (English), preliminary test and field test. The Chinese version of the IH-QOL has been demonstrated to have good internal consistency in patients with IH.

#### *20.3.2 Pediatric Quality of Life Inventory 4.0 family impact module*

The Pediatric Quality of Life Inventory 4.0 family impact module (PedsQL™ 4.0 FIM), which was developed by Varni et al., is used to measure the impact of pediatric chronic disease on family functioning. The PedsQL™ FIM can stand alone or be integrated into the other measurement model, allowing an overall assessment of QOL in children and their parents. Chen et al. translated it cross-culturally into a Chinese version. The Chinese version of the PedsQL™ FIM demonstrates good internal consistency and discriminant and construct validity. The FIM is a parent-reported instrument that measures the impact of chronic health conditions on children's health-related QOL (HRQOL) and their family functioning. This instrument is composed of 9 dimensions and 37 items. The dimensions include physical functioning (6 items), emotional functioning (5 items), social functioning (4 items), cognitive functioning (5 items), communication (3 items), worry (5 items), daily activities (3 items), family relationships (5 items) and financial issues (1 item). The first six dimensions measure parent self-reported HRQOL, while the latter three dimensions measure parent-reported family functions.

#### *20.3.3 Procedures*

The site investigators are trained by the project managers to guarantee the quality of the investigation. Before completing the questionnaires, the site investigators provided a good explanation of the purpose and significance of the questionnaires. Under the supervision of site investigators, when necessary, the site investigators

---

explained the study to the parents individually. If the parents had questions related to semantic or conceptual understanding, the site investigators assisted the parents in completing the questionnaires. In addition, the site investigators were responsible for ensuring that there were no missing data in the questionnaires.

In two questionnaires, standardized response choices consisted of five categories scored from 0 to 4. Likert-type scale responses were provided for each item: 0 = never a problem; 1 = almost never a problem; 2 = sometimes a problem; 3 = often a problem; and 4 = almost always a problem. The items were then linearly transformed to a 0-100 scale (0 = 100, 1 = 75, 2 = 50, 3 = 25, 4 = 0), with higher scores indicating better HRQOL. The dimension scores are computed as the sum of the items divided by the number of items answered within a particular dimension.

#### ***20.4 Complete healing time of ulceration***

Additional information was collected by site investigators for patients with ulceration. Ulceration is defined as a break in the integrity of the hemangioma surface epithelium (or skin) with or without infection. The information included the extent of ulceration, complications of ulceration, prior duration of ulceration (before treatment), concurrent treatments, and complete healing time. Prior duration of ulceration was defined as the time from the first sign of ulceration until before  $\beta$ -blocker treatment. The complete healing time of the ulceration was defined as the time from the first dosage of propranolol or atenolol until complete healing of the hemangioma ulceration. Concurrent treatments, including oral pain medication, oral antibiotics, topical ointment antibiotics and/or wound dressings, were permitted to treat ulcerated IH and were recorded.

#### ***20.5 Rebound rate***

Regrowth of more than 20% in hemangioma appearance (including changes in color and/or volume) after stopping the medication was considered significant rebound. The inclusion criteria for rebound analysis were as follows: (1) patients who completed 6 months of treatment and (2) patients who discontinued therapy or were tapering treatment after achieving an any response. The exclusion criteria were as follows: (1) patients who were noncompliant with treatment and (2) patients who did not respond to treatment. Whether a patient had hemangioma rebound was based on the site investigators' assessments after the week 24 treatment. In patients with

---

significant rebound, reinitiation of systemic therapy (either propranolol or atenolol) was recommended. Minor rebound, which was defined as those patients in whose rebound was noted but no reinitiation of systemic therapy or further treatment was necessary, was not included in the analysis.

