### ***17.2 Rebound management***

Significant rebound after stopping the medication was treated by reinstitution of daily therapy with either propranolol (2 mg/kg per day) or atenolol (1 mg/kg per day) until hemangioma remission.

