**22 Tapering and discontinuation of treatment**

Propranolol or atenolol were tapered and stopped at an appropriate time, which was primarily based on the response and lesion regression after treatment. In this trial, the treatment was tapered and discontinued on complete or nearly complete resolution of IH or if no further improvement of IH (for 12 weeks of observation) was observed after month 6. At the end of the treatment period, the drug dose was gradually reduced over 4 weeks and then cease. For more detail regarding the procedures for tapering and discontinuation of treatment, refer to the **Treatment** section.

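### Significant rebound is defined by extent and excluded minor rebound by need for treatment, and a crude rate over unequal time off drug could differ between arms without a drug effect

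*Combined protocol and SAP*

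**What the plan says.** Section 20.5 defines the event by extent: "Regrowth of more than 20% in hemangioma appearance (including changes in color and/or volume) after stopping the medication was considered significant rebound". It defines minor rebound by management, as cases where "rebound was noted but no reinitiation of systemic therapy or further treatment was necessary, was not included in the analysis". For significant rebound, the same section says that "reinitiation of systemic therapy (either propranolol or atenolol) was recommended". Section 17.2 puts it differently: "Significant rebound after stopping the medication was treated by reinstitution of daily therapy".

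The rebound set in Section 20.5 consists of infants who completed 6 months of treatment and of "patients who discontinued therapy or were tapering treatment after achieving an any response". Noncompliant infants and nonresponders are excluded. Site investigators judge rebound. The trial is open-label (Section 6), and Section 18 schedules no central photographs between weeks 24 and 96.

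Treatment lasts at least 6 months, with no stated maximum (Section 17.1). Under Section 22, "the treatment was tapered and discontinued on complete or nearly complete resolution of IH", or after 12 weeks without further improvement beyond month 6, and the taper takes 4 weeks. Follow-up runs for 96 weeks from the start of treatment, not from its end (Section 9).

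Section 25.4 gives Fisher's exact or chi-square for categorical variables and Kaplan-Meier only for time to treatment discontinuation. It also states: "All secondary outcomes were analyzed based on the intention-to-treat principle".

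**The concern.** There are two separate problems.

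The first is classification. One category is set by size and the other by whether treatment was needed, so they do not divide the cases cleanly. Whether a regrowth above 20% counts can turn on a treatment judgement made by someone who knows the drug.

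The second is time at risk. An infant who stops early is watched off drug for longer than one who stops late, and so has more opportunity to rebound. A simple proportion takes no account of this. Stopping is driven by response, so a drug that worked sooner could show more rebound only because its infants were observed off drug for longer.

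Rebound is a named secondary outcome in a comparison expected to support first-line use of atenolol, so the rate will be read as a drug comparison.

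**Working it through.** The documents give no expected rebound rate or power for rebound, so there is no planned figure to reproduce.

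**Step 1: the definitions side by side (Section 20.5).**

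| Regrowth | Treatment judged necessary | Treatment judged not necessary |
|---|---|---|
| Above 20% | Significant | Significant by extent, minor by management |
| 20% or less | Neither definition fits | Minor |

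The top right cell is the overlap. Section 20.5 does not say which definition prevails there, nor whether minor cases leave the numerator only or the denominator too. An infant for whom retreatment was advised but declined is not literally minor, so the overlap is narrower than all untreated cases.

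An illustration of sensitivity, with every input assumed: true regrowth above 20% in 20% of each arm, with all such cases judged to need treatment in one arm and 60% in the other.
- Minor cases out of the numerator only: 0.20 × 0.60 = 12%, against 20%.
- Minor cases out of both: 0.12 / (1 − 0.08) = 13%, against 20%.

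**Step 2: event against analysis set.** Rebound is counted after stopping, but infants still tapering are in the set. Read literally, they cannot yet have the event.

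**Step 3: time off drug.** Weeks off drug by week 96 = 96 − (taper start + 4). The 4-week taper is from Section 22. Taper is assumed to start at a scheduled visit, and visits are 12 weeks apart after week 24 (Section 16).
- Taper starts at week 24: 96 − 28 = 68 weeks
- Taper starts at week 36: 96 − 40 = 56 weeks
- Taper starts at week 48: 96 − 52 = 44 weeks

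**Step 4: effect on a crude rate.** Assume one constant hazard for both drugs, with 15% rebound by 48 weeks off drug. Neither assumption comes from the documents. Then λ = −ln(0.85)/48 = 0.003386 per week, and risk = 1 − exp(−λ × weeks off drug).

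| Weeks off drug | Risk |
|---|---|
| 68 | 20.6% |
| 60 | 18.4% |
| 56 | 17.3% |
| 44 | 13.8% |

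- Whole arms at 68 and 56 weeks: 20.6 − 17.3 = 3.3 points with no drug difference.
- Arm means 4 weeks apart (60 and 56): 18.4 − 17.3 = 1.1 points. With an assumed 150 infants per arm, the standard error of a difference near 18% is √(2 × 0.18 × 0.82 / 150) = 4.4 points.

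**Step 5: effect on the test.** With 150 per arm, equal constant hazards and an assumed 52-week risk of 10% to 30%, a nominal 5% two-proportion test finds a false difference in about 9% to 17% of trials if one whole arm tapers from week 24 and the other from week 36. With equal stopping times it keeps its 5%.

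**The case against.** The strongest reply on classification is Section 17.2. If significant rebound was always treated, then significant means above 20% and retreated, minor means less than that, and the overlap is empty in practice. That reading is fair, and it may make the overlap small. It does not remove the ambiguity, because Section 20.5 only recommends retreatment and puts no ceiling on minor.

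On time at risk, nothing in the documents shows that the arms stop at different times. A 3.3-point gap needs whole arms 12 weeks apart, and a modest difference in means gives about 1 point, well inside sampling error. If rebound clusters soon after stopping, infants with 44 weeks or more off drug have all passed through that period and the gap shrinks toward zero. The planned Kaplan-Meier curves of treatment discontinuation would also show an imbalance in stopping time. All of this stands as a limit on size. But those curves would reveal an imbalance without correcting the rebound comparison for it.

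No test is named for rebound itself, so the crude comparison is inferred from its description as a rate and from Section 25.4. That inference is reasonable, since no other method is offered.

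On the population, a reader might infer that restricting to responders breaches the intention-to-treat sentence in Section 25.4. The documents do not require that reading. Rebound has no meaning in an infant who never responded or never stopped, and the sentence can mean analysis by assigned arm. What remains open is the removal of noncompliant infants, and the lack of any statement that this set is an exception.

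**Conclusion.** The point holds as a weakness in the definition and analysis of one secondary outcome. The overlap between the two rebound categories, and the differing accounts of retreatment in Sections 17.2 and 20.5, are plain from the text. Unequal time off drug between infants is built into the design.

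Two stronger readings are not supported. A reader might infer that regrowth above 20% left untreated is definitely dropped. The text does not say which definition prevails, and it turns on treatment not being necessary, not on treatment not being given. A reader might also infer that the comparison is biased, or biased in a known direction. Imbalance between arms is possible but not shown.

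The size depends on the assumed constant hazard, the assumed 15% by 48 weeks and the assumed stopping times: about 1 point for a 4-week difference in arm means, and 3.3 points if whole arms differ by 12 weeks. The week-24 primary result is not affected.

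**What to change.** For the outcome analysis only, with no change to dose, taper or retreatment:

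1. Classify rebound by the 20% extent criterion alone, whether or not the infant was retreated. Have sites record that judgement for every rebound noted.
2. Reconcile Sections 17.2 and 20.5 on how significant rebound was handled.
3. Among responders who stopped, analyse time from last dose to significant rebound by Kaplan-Meier and log-rank, censored at the last visit. Infants still tapering enter when they stop, which keeps the clock consistent with an event defined after stopping.
4. Keep noncompliant responders in, at least as a sensitivity analysis.
5. Label the set as a post-randomisation subset and an explicit exception to the intention-to-treat sentence in Section 25.4.

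Rebound as a share of all randomised infants would not be a good companion figure. It counts infants still on drug as rebound-free and so favours the arm kept on drug longer.

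The cost is mainly wording, plus one item on the report form, because no section says that extent is recorded for cases called minor. The rebound rate may look slightly higher. Site assessment of the 20% threshold stays unblinded, and the log-rank test still compares subsets formed after randomisation. Both should be stated as limitations.
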